6. STUDY DESIGN

This study is a prospective, multicenter, randomized controlled trial of the FlowTriever System compared to CDT for acute PE, and includes a non-randomized cohort for subjects with an absolute contraindication to thrombolytics. The study will collect data on demographics, comorbidities, details from the PE diagnosis and treatment, and clinical outcomes through 30-day follow up.

Randomized Controlled Trial Cohort (RCT Cohort):

This study is a prospective, multicenter, randomized controlled trial of the FlowTriever System compared to Catheter-Directed Thrombolysis (CDT) for treatment of acute PE.

Non-Randomized Absolute Contraindication to Thrombolytics Cohort (Contraindication Cohort):

Subjects who meet study eligibility criteria and who have an absolute contraindication to thrombolytics, whose initial planned primary treatment strategy includes FlowTriever, will be evaluated as part of the Contraindication Cohort. The same RCT Cohort clinical assessments and follow up schedule will be administered in this Contraindication Cohort.

STUDY POPULATION

RCT Cohort: Up to 550 subjects with acute PE will be enrolled and randomized at up to 60 study sites. All subjects who sign informed consent and who meet all of the inclusion criteria and none of the exclusion criteria will be randomized (1:1, FlowTriever or CDT).

- One-to-one (1:1) randomization will be stratified by bleeding risk, as measured by the VTE-BLEED score³.

Table 1 VTE-BLEED Algorithm

Parameter	Points
Active cancer	2
Male patient with uncontrolled hypertension (≥ 140 mmHg)	1
Anemia	1.5
History of bleeding	1.5
Renal dysfunction (Cr clearance 30-60 ml/min)	1.5
Age ≥ 60 years	1.5
TOTAL ≥ 2 indicates higher risk of bleeding on stable AC vs <2	9

- Stratification by the VTE-BLEED algorithm will occur automatically in the Electronic Data Capture (EDC) system upon data entry, and randomization will be assigned accordingly.

Contraindication Cohort: Up to 150 additional subjects who meet study eligibility criteria and who have an absolute contraindication to thrombolytics, whose initial planned primary treatment strategy includes FlowTriever, will be evaluated as part of the Contraindication Cohort. The same RCT Cohort clinical assessments and follow up schedule will be administered in this Contraindication Cohort.

POINT OF ENROLLMENT

To participate in the study, the patient must sign the informed consent. If a subject signs the informed consent but is later deemed NOT to meet the invasive systolic PA pressure eligibility criteria, the subject would be considered a screen failure and not enrolled in either the RCT Cohort or the Contraindication Cohort. Screen failures will be tracked in the EDC system with rationale for the screen failure. The point of enrollment is when the subject meets all eligibility criteria and study device enters the subject's body.

Enrollment considerations in study design

Any patient with a documented **absolute contraindication** to thrombolytics will be excluded from the RCT Cohort but may be enrolled in the Contraindication Cohort if treated with FlowTriever. Absolute contraindications include (per ESC Guidelines 2019¹ and AHA Scientific Statements 2019):

[figure not shown]
- History of hemorrhagic stroke or stroke of unknown origin
- Ischemic stroke in previous 6 months
- Presence of intracranial conditions that may increase the risk of bleeding, such as neoplasms, arteriovenous malformations, or aneurysms
- Recent (within 3 months) intracranial or intraspinal surgery or serious head trauma
- Bleeding diathesis
- Active internal bleeding, excluding menses
- Aortic dissection

- Severe uncontrolled hypertension
- Any other condition listed as an absolute contraindication on the product label for the thrombolytic agent planned for use by local standard and investigator discretion

Subjects with a **relative contraindication** to thrombolytics are eligible for the RCT Cohort per protocol. Subjects with **only** relative contraindication(s) to thrombolytics are *not* eligible for the Contraindication Cohort. Relative contraindications include:

- Transient ischemic attack in previous 6 months
- Oral anticoagulation, except for aspirin
- Therapeutic LMWH within 24 hours
- Pregnancy or first post-partum week
- Non-compressible puncture sites
- Traumatic resuscitation, defined as prolonged (>10 min) cardiopulmonary resuscitation
- Refractory hypertension (systolic BP >180 mmHg or diastolic BP >110 mmHg) on two confirmed measurements
- Advanced liver disease
- Infective endocarditis
- Active peptic ulcer
- Recent administration of glycoprotein (GP) IIb/IIIa inhibitors
- Anemia (e.g. hemoglobin <10 g/dL)

Figure 9 Subject Enrollment Flowchart

INCLUSION CRITERIA

Subjects must meet each of the following criteria to be included in the study:

1. Age \geq 18 years
2. Echo, computed tomographic pulmonary angiography (CTPA), or pulmonary angiographic evidence of any proximal filling defect in at least one main or lobar pulmonary artery
3. Including ALL of the following:
 - a. Clinical signs and symptoms consistent with acute PE, or PESI class III-V, or sPESI \geq 1
AND
 - b. Hemodynamically stable
AND
 - c. RV dysfunction on echocardiography or CT
AND
 - d. Any one or more of the following present at the time of diagnosis:
 - i. Elevated cardiac troponin levels
 - ii. History of heart failure
 - iii. History of chronic lung disease
 - iv. Heart rate \geq 110 beats per minute
 - v. SBP $<$ 100mmHg
 - vi. Respiratory rate \geq 30 breaths per minute
 - vii. O₂ saturation $<$ 90%
 - viii. Syncope related to PE
 - ix. Elevated lactate
4. Intervention planned to begin within 72 hours of the later of either
 - a. Confirmed PE diagnosis
OR
 - b. If transferring from another hospital, arrival at the treating hospital
5. Symptom onset within 14 days of confirmed PE diagnosis

EXCLUSION CRITERIA

Subjects will be excluded from the study for any of the following criteria:

1. Unable to anticoagulate with heparin, enoxaparin or other parenteral antithrombin
2. Index presentation with hemodynamic instability that are part of the high-risk PE definition in the ESC Guidelines 2019¹, including ANY of the following:
 - a. Cardiac arrest
OR
 - b. Systolic BP $<$ 90 mmHg or vasopressors required to achieve a BP \geq 90 mmHg despite adequate filling status, AND end-organ hypoperfusion
OR
 - c. Systolic BP $<$ 90 mmHg or systolic BP drop \geq 40 mmHg, lasting longer than 15 min and not caused by new-onset arrhythmia, hypovolemia, or sepsis
3. Known sensitivity to radiographic contrast agents that, in the Investigator's opinion, cannot be adequately pre-treated
4. Imaging evidence or other evidence that suggests, in the opinion of the Investigator, the patient is not appropriate for catheter-based intervention (e.g., inability to navigate to target location, clot limited to segmental/subsegmental distribution, predominately chronic clot)
5. Patient has right heart clot in transit identified at baseline screening
6. Life expectancy $<$ 30 days (e.g., stage 4 cancer or severe COVID-19 infection), as determined by the Investigator

7. Current participation in another drug or device study that, in the investigator's opinion, would interfere with participation in this study
8. Current or history of chronic thromboembolic pulmonary hypertension (CTEPH) or chronic thromboembolic disease (CTED) diagnosis, per ESC 2019 guidelines¹
9. Invasive systolic PA pressure $\geq 70\text{mmHg}$ prior to study device entering the body
10. Administration of bolus or drip/infusion thrombolytic therapy or mechanical thrombectomy for the index PE event within 48 hours prior to enrollment
11. Ventricular arrhythmias refractory to treatment at the time of enrollment
12. Known to have heparin-induced thrombocytopenia (HIT)
13. Subject has any condition for which, in the opinion of the investigator, participation would not be in the best interest of the subject (e.g., compromise the well-being or that could prevent, limit, or confound the protocol-specified assessments). This includes a contraindication to use of FlowTriever or CDT System (for example, EKOS System) per local approved labeling
14. Subject has previously completed or withdrawn from this study
15. Patient unwilling or unable to conduct the follow up visits per protocol.

7. ASSESSMENTS AND FOLLOW UP SCHEDULE

SCHEDULE OF ASSESSMENTS

The schedule of assessments comprises the assessments to be performed for all subjects enrolled in the study. Any departures from the follow up schedule will be documented as protocol deviations.

Schedule of Assessments

Assessment	Baseline (≤ 72 hrs) ^a	Index Procedure ^h (Day 0)	24 Hour Visit (24 hrs. ± 8 hrs.)	Hospital Discharge ^e	30 Day Visit (30 days + 15 days)	Unscheduled Visit
Informed Consent	X					
Inclusion/exclusion review	X					
Demographics	X					
Medical history, risk factors, and PE condition	X					
Anticoagulation regimen	X	X	X	X	X	X
Clinical labs (Hemoglobin, Troponin)	X					
Clinical labs (Hemoglobin, ACT, and PTT)		X				
Imaging (Echo or CT) ^f	X		X			
mMRC dyspnea score, Borg, and NYHA	X		X	X	X	
Oxygenation status		X ^d	X	X	X	
Invasive PA pressures (required Pre-Index Procedure)		X ^b				
Invasive PA pressures (optional Post-Index Procedure)		X ^c				
Bleeding measures		X	X	X		
Evaluation of primary endpoint components ^g				X		
PEmb-QoL and EQ-5D-5L					X	
Adverse event assessment		X	X	X	X	X

^a Baseline assessment must be done ≤ 72 hours of Index Procedure

^b Interventionalists will collect pulmonary artery pressures immediately before primary therapeutic catheter insertion.

^c Trained interventionalists will collect pulmonary artery pressures at least 10 minutes after primary therapeutic catheter (for CDT) begins therapy, or after the primary therapeutic catheter (for FlowTriever) is removed for the last time. Additional PA pressures are requested to be collected in the CDT subjects 6 hours (± 2 hours) post procedure using the same technique.

^d Collect oxygenation status just prior to index procedure

^e Note that the Discharge Visit can be done at the same time as the 24-hour visit if applicable. However, if both visits are completed at the same time, both CRFs will need to be filled out. There are no windows from Index Procedure determining when the Discharge Visit must be completed. The Discharge Visit is completed when the patient is discharged from the hospital and the assessments are completed within the 12 hours prior to discharge. If the subject has not been discharged from the hospital by the 30-day visit, then the Discharge Visit is missed and the 30-day assessment (including evaluation of primary endpoint components) and patient exit is completed.

^f Imaging can be either echo or CT, but needs to be the same modality within each patient at Baseline and 24-hour visit

^g Note that the evaluation of endpoint considerations include All-cause mortality, ICH, Major bleeding, Clinical deterioration and/or escalation to a bailout therapy, and ICU admission and ICU length-of-stay. These are assessed at hospital discharge or 7 days after the index procedure, whichever is earlier. If a subject is still in the hospital and exits the study for any reason before the 30-day Visit, evaluation of primary endpoint components should be completed at the time of patient exit.

^h The Index Procedure begins when access for treatment is obtained. The Index Procedure is considered complete upon exit from the procedure room. The time of exit from the procedure room is the time reference used for the subsequent visit windows including the 24-hour visit.

BASELINE ASSESSMENTS

The baseline assessments must be done \leq 72 hours of Index Procedure including:

- Informed consent
- Inclusion/exclusion review
- Demographics
- Medical history, risk factors, and PE condition
- Anticoagulation regimen
- Clinical labs (Hemoglobin, Troponin)
- Cardiac imaging (Echo or CT)
 - Imaging can be either echo or CT, but needs to be the same modality within each patient at baseline and 24-hour visit.
- mMRC dyspnea score, Borg, and NYHA

ALLOCATION AND RANDOMIZATION

Upon the patient meeting baseline eligibility criteria and providing informed consent, a check against the list of absolute contraindications to thrombolytics is performed (see Figure 9: Patient Enrollment Flowchart). Subjects with one or more absolute contraindications to thrombolytics and whose initial treatment plan includes FlowTriever are allocated to the Contraindication Cohort. Subjects without any absolute contraindications (whether there are relative contraindications to thrombolytics or no contraindication to thrombolytics) are allocated to the RCT Cohort.

Study sites will receive the subject randomization assignment electronically in the electronic data capture (EDC) system upon completion of baseline information used to stratify randomization using the calculated VTE-BLEED score. Subjects will be randomized to and treated with (a) mechanical thrombectomy with FlowTriever or (b) catheter-directed thrombolysis per local practice standards.

INDEX PROCEDURE

The initial catheter-based intervention for acute PE is considered the Index Procedure. The procedure is conducted under fluoroscopic/angiographic guidance. Refer to the Instructions for Use (IFU) for techniques and methods for device deployment. The following assessments are collected during the index procedure including:

- Anticoagulation regimen
- Clinical labs (Hemoglobin, ACT, and PTT collected just prior to index procedure intervention)
- Oxygenation status collected just prior to index procedure
- Invasive PA pressures (**required** pre-index procedure)
 - Interventionalists will collect pulmonary artery pressures immediately before primary therapeutic catheter insertion.
- Invasive PA pressures (**optional** post-index procedure)
 - Trained interventionalists will collect pulmonary artery pressures at least 10 minutes after primary therapeutic catheter (for CDT) begins therapy, or after the primary therapeutic catheter (for FlowTriever) is removed for the last time. Additional PA pressures are requested to be collected in the CDT subjects 6 hours (\pm 2 hours) post procedure using the same technique.
- Bleeding measures
- Adverse event assessment

The Index Procedure begins when access for treatment is obtained. The Index Procedure is considered complete upon exit from the procedure room. The time of exit from the procedure room is the time reference used for the subsequent visit windows including the 24-hour visit. The 7-day maximum for in-hospital primary endpoint

assessment is defined as 168 hours from the end of the Index Procedure. The 30-day Visit window refers to 30 calendar days from the day the Index Procedure ends.

Recommendations for Anticoagulation Management and Thrombolytic Therapy

In order to approximate real-world practice, the use of pre-procedure, intra-procedure, and post-procedure anticoagulation should be guided by investigator discretion, local standard of care, and in accordance with IFU for the assigned therapy.

Similarly, dose and duration of thrombolytic agents in subjects assigned to CDT is guided by investigator discretion, local standard of care, and in accordance with IFU. Initial dosing strategy should be recorded in the corresponding CRF, along with any changes in dose throughout the infusion, including extended infusion times. Bolus thrombolytics that are part of initial treatment plan are not considered bailout, although bolus lytics are discouraged in subjects assigned to FlowTriever therapy.

Suggested PTT target to avoid bleeding during CDT, per SEATTLE-II, is PTT 40-60s.

FOLLOW UP ASSESSMENTS

Follow up evaluations will include the 24-hour visit (24 hrs \pm 8 hrs), hospital discharge, and the 30-day visit (30 days \pm 15 days). All windows reference time from Index Procedure completion (defined as time of exit from the procedure room).

24-hour visit: The following assessments will be performed at the 24-hour visit:

- Anticoagulation regimen
- Cardiac imaging (Echo or CT required)
 - Imaging can be either echo or CT, but needs to be the same modality within each patient at baseline and 24-hour visit.
- Oxygenation status
- mMRC dyspnea score, Borg, and NYHA
- Bleeding measures
- Adverse event assessment

Note that the discharge visit can be done at the same time as the 24-hour visit if applicable. However, if both visits are completed at the same time, both CRFs will need to be filled out.

Discharge visit: The following assessments will be performed at the discharge visit:

- Anticoagulation regimen
- mMRC dyspnea score, Borg, and NYHA
- Oxygenation status
- Bleeding Measures
- Evaluation of primary endpoint components including all-cause mortality, ICH, major bleeding, clinical deterioration and/or escalation to a bailout therapy, and ICU admission and ICU length-of-stay
- Adverse event assessment

Note that the Discharge Visit can be done at the same time as the 24-hour visit or the 30-day visit, if applicable. However, if two visits are completed on the same day, both CRFs will need to be filled out. There are no windows from Index Procedure determining when the Discharge Visit must be completed. Rather, the Discharge Visit is

completed when the patient is discharged from the hospital and the assessments are completed within the 12 hours prior to discharge. If the subject has not been discharged from the hospital by the 30-day visit, then the Discharge Visit is missed and the 30-day assessment (including evaluation of primary endpoint components) and patient exit is completed.

Note that the evaluation of endpoint considerations include All-cause mortality, ICH, Major bleeding, Clinical deterioration and/or escalation to a bailout therapy, and ICU admission and ICU length-of-stay. These are assessed at hospital discharge or 7 days after the index procedure, whichever is earlier. If a subject is still in the hospital and exits the study for any reason before the 30-day Visit, evaluation of primary endpoint components should be completed at the time of patient exit.

30-day visit: The following assessments will be performed at the 30 day visit (30 days +15 days):

- Anticoagulation regimen
- mMRC dyspnea score, Borg, and NYHA
- Oxygenation status
- PEmb-QoL and EQ-5D-5L
- Adverse event assessment

The 30-day visit assessments can be conducted in-person or remotely, if allowed by the IRB/EC.

The patient will be exited from the study at this visit if not already exited earlier for other reasons.

Note that the evaluation of endpoint considerations include All-cause mortality, ICH, Major bleeding, Clinical deterioration and/or escalation to a bailout therapy, and ICU admission and ICU length-of-stay. These are assessed at hospital discharge or 7 days after the index procedure, whichever is earlier. If a subject is still in the hospital and exits the study for any reason before the 30-day Visit, evaluation of primary endpoint components should be completed at the time of patient exit.

UNSCHEDULED FOLLOW UP VISITS

The study will only record subject visits during the follow up period (defined as discharge through completion of the 30-day visit, up to a maximum 45 days from Index Procedure) that are related to the patient's PE condition and treatment. The following assessments will be performed at the unscheduled visit:

- Anticoagulation regimen
- Adverse event assessment

WITHDRAWALS AND LOST TO FOLLOW UP

Participation is completely voluntary, and each subject is free to withdraw consent to participate in the study at any time. An investigator also has the right to withdraw the subject from the study for reasons concerning the health or well-being of the subject, or in the case of lack of cooperation. Should a subject decide to withdraw consent for any reason, or should the investigator decide to withdraw the subject, all efforts will be made to complete and report the observations up to the time of withdrawal as thoroughly as possible. A complete final evaluation at the time of the subject's withdrawal must be made and an explanation given as to why the subject is withdrawing or being withdrawn from the study.

The reason for, and date of, withdrawal must be recorded on the subject's Study Exit CRF. If the reason for the withdrawal is a device, drug, or procedure-related AE, the event must be reported to the Sponsor and recorded in the CRF.

If the index catheter-based intervention procedure is aborted before treatment catheter insertion or is not performed, the subject is considered a screen fail.

All efforts will be made to return subjects for all follow up visits. Due diligence in reaching the subject must be made by two documented telephone contact attempts, emails, or regular postal mail letters. After the above attempts are made, if no response from the subject or their designated caregiver is obtained, the final evaluation of the subject and study exit will be dated on the last visit at which study-related assessments were performed. The Study Exit CRF page will be completed, and communication attempts will be documented.

COVID-19 EFFECT ON RESEARCH

This study was designed to compare the clinical outcomes of patients treated with the FlowTriever System versus Catheter-Directed Thrombolysis (CDT) for use in acute pulmonary embolism (PE). As a result of the COVID-19 pandemic, clinical practice patterns may be affected, and subject visits may be postponed or eliminated. Additionally, subjects may not be willing to be seen by their provider potentially exposing both parties to the virus. In order to protect subject and provider safety, some data may be collected from subjects over the phone if allowed by the IRB/EC.

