The FlowTriever System is a single-use over-the-wire catheter-based system for the minimally invasive treatment of thromboemboli in the peripheral vasculature and the treatment of pulmonary embolism. The FlowTriever System is composed of two main components: the Triever aspiration catheter and the FlowTriever catheter. The FlowTriever System can be used in conjunction with the FlowSaver™ Blood Return System, which is a separate product for filtering and reintroducing blood aspirated by the FlowTriever System. Each of these devices is described below.

Triever™ Aspiration Catheters

The Triever Aspiration Catheter is a large-bore catheter used primarily for controlled aspiration of thromboemboli (Fig. 2A). The catheters are available in 16, 20, and 24Fr diameters, which are referred to as the Triever16™ (T16), Triever20™ (T20), and Triever24™ (T24) catheters, respectively. The Triever20 Curve™ (T20 Curve) pre-shaped catheter is designed with a bend of up to 260° to provide access to challenging anatomy (Fig. 2B) and must be used coaxially with the T24 catheter. After the distal end of the Triever catheter is positioned adjacent to thrombus, a vacuum is applied to the closed catheter side port via a 60 mL custom large-bore syringe (Fig. 3). Opening the side port valve produces an abrupt, high-flow suction to extract thrombus through the Triever catheter and into the syringe, while limiting blood loss to 60 mL per aspiration.

Figure 2 Triever Catheters

[figure not shown]

Figure 3 Large Bore Syringe

[figure not shown]

FlowTriever™ Catheter

The FlowTriever catheter, which is designed to be deployed coaxially through the Triever Catheter, consists of a flexible shaft attached to distal self-expanding nitinol disks. It is used to macerate and deliver thrombus to the Triever catheter for removal via aspiration and is often used for more chronic, wall-adherent thrombus. The

FlowTriever catheter is available in multiple configurations. One representative version of the FlowTriever catheter consists of 3 disks (Fig. 4) that are available in four sizes ranging in disk diameters from 12.5 to 28.0mm.

Figure 4 FlowTriever Catheter (3-disk Configuration Shown)

[figure not shown]

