Additional FlowTriever catheters that have different nitinol disk configurations may be used during the course of this study depending on the status of regulatory clearances local to each geographic region in which the study is conducted. All FlowTriever catheter configurations have the same function to macerate and deliver thrombus to the Triever catheter for aspiration.

A complete description of the FlowTriever System is provided in the Instructions for Use.

FlowSaver™ Blood Return System

The FlowSaver Blood Return System is used to filter the aspirated contents of the Large Bore Syringe from a FlowTriever System procedure. The provided 60cc syringe is connected to the outlet port and used to aspirate blood through the 40 μ m filter (Fig. 5). The filtered blood is then re-introduced to the patient through a sheath or catheter. It is indicated to be used with the Triever Catheters for autologous blood transfusion.

Figure 5 The FlowSaver Blood Return System

A complete description of the FlowSaver System is provided in the Instructions for Use (FlowSaver is FDA-cleared in the United States under 510(k) number K210176).

CATHETER-DIRECTED THROMBOLYSIS (CDT)

Catheter-directed thrombolysis devices are catheters introduced endovascularly and placed at the site of the thrombus for localized infusion of thrombolytic drugs, such as various tissue plasminogen activators (tPA), which are infused through side holes in the catheter to enhance thrombus dissolution. Due to the bleeding risks associated with thrombolytic drugs, patients undergoing CDT are typically admitted to the ICU and immobilized during the infusion, then returned to the catheterization lab to assess the degree of thrombus dissolution following treatment. Additional thrombolytic infusions may be attempted if the initial infusion resulted in insufficient thrombus dissolution.

Various commercially available endovascular catheters may be used for CDT purposes, including both conventional CDT catheters and ultrasound-assisted CDT catheters. These two categories of CDT devices are described briefly in the following sections.

[figure not shown]
Conventional CDT Catheters

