5. OUTCOME VARIABLES

PRIMARY ENDPOINT DEFINITION

The primary endpoint is a composite clinical endpoint constructed as a win ratio, a hierarchy of the following, which are assessed at hospital discharge or at 7 days after the index procedure, whichever is sooner:

1. All-cause mortality, or
2. Intracranial hemorrhage (ICH), or
3. Major bleeding per ISTH definition⁴, or
4. Clinical deterioration defined by hemodynamic or respiratory worsening, and/or escalation to a bailout therapy, or
5. ICU admission and ICU length-of-stay during the index hospitalization and following the index procedure.

Definition of Intracranial Hemorrhage

Intracranial hemorrhage (ICH) is defined as ANY bleeding involving the brain parenchyma, ventricular system, or subarachnoid, subdural, or epidural regions, as identified by CT scan or MRI, regardless of symptoms.

Definition of Major Bleeding

Major bleeding is defined according to the International Society for Thrombosis and Haemostasis (ISTH) definition of major bleeding in non-surgical subjects⁴.

1. Fatal bleeding, and/or
2. Symptomatic bleeding in a critical area or organ, such as intracranial, intraspinal, intraocular, retroperitoneal, intraarticular or pericardial, or intramuscular with compartment syndrome, and/or
3. Bleeding causing a fall in hemoglobin level of 2 g/dL (1.24 mmol/L) or more, or leading to transfusion of two or more units of whole blood or red cells.

Definitions of Clinical Deterioration and Bailout

Clinical deterioration is defined as documented objective hemodynamic or respiratory worsening that is new (i.e. not present at the time of enrollment).

Clinical deterioration is when one or more of the following is definitively documented, with relation to both the severity and the duration of the event:

- Hypotension with systolic blood pressure <90 mm Hg lasting at least 30 minutes, unresponsive to fluid resuscitation, and requiring the addition of or increased dose of vasopressors

- Fall in systolic blood pressure by 40 mm Hg or more, lasting at least 30 minutes, and accompanied end-organ hypoperfusion (such as oliguria, mental status changes, ischemic extremities)
- Cardiac arrest requiring cardiopulmonary resuscitation
- Bradycardia lasting more than 10 minutes, accompanied by hypotension, and requiring pharmacologic intervention or insertion of a pacemaker
- Ventricular tachycardia or fibrillation requiring pharmacologic intervention or defibrillation

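### No post-procedure hemoglobin is specified, so detection of major bleeds defined by a 2 g/dL fall rests on local testing and may differ between arms

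*Protocol*

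**What the plan says.** **Endpoint.** Protocol Section 5 (Definition of Major Bleeding, repeated in Section 17) gives the ISTH routes: fatal bleeding, symptomatic bleeding at a critical site, transfusion of two or more units, or "Bleeding causing a fall in hemoglobin level of 2 g/dL (1.24 mmol/L) or more". The components are "assessed at hospital discharge or at 7 days after the index procedure, whichever is sooner". Major bleeding is third in the five-component primary hierarchy and in the four-component secondary composite. It is also tested alone by Fisher's exact test against the alternative that FlowTriever is lower (SAP 5.4.5), with alpha 0.05 (SAP 5.6).

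**Measurement.** In the Schedule of Assessments (Protocol Section 7), "Clinical labs (Hemoglobin, Troponin" is marked at baseline only and "Clinical labs (Hemoglobin, ACT, and PTT" in the Index Procedure column only. The Index Procedure text fixes the timing of the second: "Clinical labs (Hemoglobin, ACT, and PTT collected just prior to index procedure intervention". The 24-hour, discharge and 30-day lists name no laboratory test. "Bleeding measures" is listed at the index procedure, 24 hours and discharge, but neither document says what it contains.

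**Setting.** Protocol Section 2 says that "patients undergoing CDT are typically admitted to the ICU and immobilized during the infusion". Section 1 presents thrombectomy as not needing that ICU stay. SAP Section 2 calls the trial open-label, and Protocol Section 9 has the Clinical Events Committee (CEC) adjudicate data reported by sites.

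**The concern.** A fall cannot be established without a value after treatment, and a site that follows the schedule exactly need not have one. Whether a 2 g/dL fall is seen then depends on who happens to have a blood count.

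The two arms are cared for in different settings, by the Protocol's own account. If CDT patients are tested more often, some bleeds of the same size will be counted under CDT and missed under FlowTriever. The CEC cannot adjudicate a fall that was not measured. Such a case is recorded as no bleed rather than as missing, so neither the multiple imputation in SAP Section 4 nor the ITT/PP comparison in SAP 5.3 would reveal it. At stake are the major-bleeding test and the four-component composite and, to a smaller degree, the primary.

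**Working it through.** **1. No stated figure is in dispute.** The required 432 subjects (216 per arm) cannot be rebuilt, because neither document gives the component proportions behind it. The check is of the schedule, followed by an illustration of size.

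**2. Hemoglobin by time point.**

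| Time point | Hemoglobin named? | Bleeding-measures item |
|---|---|---|
| Baseline | yes | no |
| Index procedure | yes, before the intervention | yes |
| 24 hours | no | yes |
| Discharge | no | yes |
| 30 days | no | no |

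Both named values are pre-treatment. The Protocol does not say which is the reference for the fall. The Index Procedure list gives the hemoglobin labs and the bleeding-measures item as separate entries, which suggests that the second does not include the first, though it does not prove it.

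**3. Why testing could differ.** CDT patients are typically in the ICU during infusion. The sponsor's all-comer FlowTriever registry reports a median ICU stay of 0.0 days (Section 3, FLASH Interim Results). Section 7 suggests a PTT target during CDT, which implies blood draws. The window closes at discharge, so a shorter stay leaves fewer chances for an incidental count. Falls are possible in the FlowTriever arm too: Section 2 describes the device as "limiting blood loss to 60 mL per aspiration", although the FlowSaver system can return filtered blood.

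**4. Size of a spurious difference.** Let h be the true rate, equal in both arms, of bleeds that qualify only through a hemoglobin fall, and let d be the chance that such a fall is measured.

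Spurious difference = h × (d_CDT − d_FT)

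Testing rates are not in the documents; 0.95 and 0.70 are assumed.
- h = 1.3%: 1.3 × 0.25 = 0.33 points. (1.3% is the registry's rate of all major bleeds through 48 hours.)
- h = 4%: 4 × 0.25 = 1.0 point. (4% is the lower of the two literature rates of all major bleeding, 4% and 10%, in Section 3.)

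**5. Effect on the tests.** Null trials were simulated with 275 per arm and the Finkelstein-Schoenfeld statistic, rejecting when z > 1.96. For the three middle rows, h is total true major bleeding times the share found only by hemoglobin. The other assumed inputs, equal in both arms, are death 1.5%, ICH 0.5%, deterioration 5%, and ICU categories 40/20/40%.

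| h per arm | Shift (points) | Four-component | Primary | Fisher, major bleeding (0.05) |
|---|---|---|---|---|
| 1.3% | 0.33 | 3.2-3.4% | 2.8-3.3% | not run |
| 2.0% (4% × 0.5) | 0.50 | 3.2% | 3.3% | 6.9% |
| 3.2% (4% × 0.8) | 0.80 | 5.3% | 3.3% | 9.9% |
| 3.5% (7% × 0.5) | 0.88 | 4.8% | 3.7% | 8.3% |
| 4.0% | 1.0 | 5.9% | 4.0% | not run |

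The middle rows use 4,000 replicates (1,500 for Fisher), the 1.3% row 6,000 and the 4.0% row 1,500. A repeat run with the component rates above agreed with both end rows to within Monte Carlo error. That error is about 0.5 points for the middle rows, so the smallest shifts in the primary cannot be told from 2.5%.

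**6. Controls, for the three middle rows.** With detection of 0.9 in both arms, the rates are 2.2-2.9% (four-component), 2.3-3.1% (primary) and 2.5-3.4% (Fisher). With detection reversed (0.95 FlowTriever, 0.70 CDT), false positives in favour of FlowTriever fall to 1.3-1.6% (four-component) and 1.5-1.8% (primary). The direction is therefore an input and not a result.

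**The case against.** A reader might infer that bleeds **are** found more often in the CDT arm, or that the trial is biased toward FlowTriever. The documents do not support that. They give no draw frequency for either arm, and step 6 shows that the sign follows the assumption.

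Other points on that side:
- **The bleeding item may include hemoglobin.** The case report forms are not in the documents, and the Protocol's abbreviation list contains entries for hemoglobin and estimated blood loss. This stands as a reason to say that no post-procedure value is *specified*, rather than that none is taken. It does not remove the need to define the item.
- **The criterion is bleeding that causes a fall.** A laboratory drop without bleeding does not qualify, bleeding is looked for in both arms, and the other ISTH routes depend less on routine counts. This stands: only bleeds that rest on hemoglobin alone are exposed.
- **These are inpatients.** The registry's median post-procedure stay is 3.0 days, so many FlowTriever patients may well be tested, and 70% is unsupported. This stands, which is why the result is an illustration. A 2-point shift would need h = 2 / 0.25 = 8% in each arm, which is hard to reconcile with the registry's 1.3%.
- **Care by local practice is a declared choice.** Section 7 says so for anticoagulation and lytic dosing. That covers treatment and does not extend to how an endpoint criterion is measured.

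**Conclusion.** The gap is real: following the schedule as written yields no common post-treatment hemoglobin for a criterion that by itself defines major bleeding. Detection is left to local practice in an open-label trial whose arms differ in expected ICU use. A difference in FlowTriever's favour is plausible but not shown.

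Under assumed testing of 95% versus 70% and h of 1.3% to 4%, the false-positive rate is about 3-6% for the four-component composite and about 3-4% for the primary, against 2.5%. The single Fisher test of major bleeding is the most exposed: 7-10% at alpha 0.05 in the rows where it was run, against about 3% with equal detection. The effect on the primary is small. These sizes rest on the assumed testing rates, the assumed share of hemoglobin-only bleeds and the assumed component rates. The point is worth acting on because the remedy is cheap and because, without it, an observed bleeding advantage could not be separated from a testing difference.

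**What to change.** 1. **Protocol.** Name a hemoglobin at the 24-hour visit in both arms, define the bleeding-measures item, and state which of the two pre-treatment values is the reference for the fall.
2. **SAP.** Keep CEC adjudication by the ISTH definition on all available data as the main analysis. Pre-specify sensitivity analyses of major bleeding, the four-component composite and the primary that (a) leave out bleeds qualifying only by a hemoglobin fall and (b) for subjects with the scheduled draw, count hemoglobin-only bleeds from that common time point alone. Adding clinically driven values to the scheduled one would bring the unequal sampling back, so (b) should exclude them.
3. **Reporting.** Give the number of post-procedure hemoglobin values per subject by arm.

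**Cost.** One routine blood count at a visit that already requires imaging, a CRF field, and an amendment needing IRB/EC approval. If it is made mid-trial there will be two ascertainment periods. For subjects already enrolled, 2(a) and 3 need only SAP wording.

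**Limits.** Analysis (a) also drops genuine bleeds. Analysis (b) gives comparability rather than completeness: Section 1 says lytic infusion can last up to 48 hours, so a 24-hour draw can precede later falls. Both should be read beside the main analysis.
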